PI	Principal Investigator
REDCap	Research Electronic Data Capture
SAE	Serious Adverse Event
SUSAR	Suspected Unexpected Serious Adverse Reaction
UIRTSO	Unanticipated Problem Involving Risks to Subjects or Others
WCM	Weill Cornell Medicine
WCINYP	Weill Cornell Imaging NewYork Presbyterian
PCa	Prostate Adenocarcinoma
⁶⁸Ga	Gallium-68
PET	Positron Emission Tomography
ROI	Regions of Interest
PSMA	Prostate Specific Membrane Antigen
Ga-PSMAcyc	Ga-PSMA cyclotron
Ga-PSMAGen	Ga-PSMA generator

1. Protocol Summary

[figure not shown]
Full Title:	Evaluation of a ⁶⁸ Ga Small Molecule PSMA Antagonist Produced by two different Methods
Clinical Phase:	I/II
Principal Investigator:	[name]
Study Description:	Patients with metastatic prostate cancer will undergo two protocol ⁶⁸ Ga-PET scans within 24-48h with ⁶⁸ Ga-PSMA-cyclotron and ⁶⁸ Ga-PSMA-generator radiotracers. The goal of the study is to evaluate repeatability and equivalence across the different ⁶⁸ Ga-PSMA production methods.
Sample Size:	Up to 30 patients will be enrolled in the study as defined by protocol criteria.
Enrollment:	30 patients will be enrolled in this study
Study Population:	Patients with metastatic prostate adenocarcinoma
Enrollment Period:	2 years
Study Design:	Single-dose, non-randomized design. Patients with metastatic prostate adenocarcinoma will be administered a single intravenous dose of each of the study drugs ⁶⁸ Ga-PSMA-cyclotron and ⁶⁸ Ga-PSMA-generator 24-48 hours apart.
Description of Sites/ Facilities Enrolling	
Participants:	This is a single site study. All study procedures will be performed in the NYP/WCMC facilities, CBIC, and WCINYP.
Study Duration:	2 years
Participant Duration:	3 Visits: 1 screening/consent and 2-infusions imaging. The duration of patient participation can be up to 4 weeks, depending on eligibility, and the scheduling and completion of required study visits
Study Agent/Device Name	
Intervention Description:	⁶⁸ Ga-PSMA-cyclotron and ⁶⁸ Ga-PSMA-generator; single dose each, approximately 100-300 mBq.
Primary Objective:	
• To evaluate equivalence of two processes to create ⁶⁸Ga-HBED-PSMA (⁶⁸Ga-PSMA-cyclotron vs. ⁶⁸Ga-PSMA-generator)
Secondary Objectives:	
• Comparative dosimetry and biodistribution (⁶⁸Ga-PSMA-cyclotron vs. ⁶⁸Ga-PSMA-generator), whole body excretion/ metabolism in patients with confirmed metastatic PCa

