Exploratory Objectives:	
• Investigate repeatability of whole-body ⁶⁸Ga-PSMA-generator Ki Patlak imaging against that of conventional whole-body ⁶⁸Ga-PSMA- SUV imaging in patients with confirmed metastatic prostate adenocarcinoma.

- Evaluate equivalence of whole-body ⁶⁸Ga-PSMA Ki Patlak imaging between the two processes to create ⁶⁸Ga-HBED-PSMA (⁶⁸GA-PSMA-cyclotron vs. ⁶⁸Ga-PSMA-generator)

Endpoints:

The primary endpoint of this study is to prove equivalence between the cyclotron and generator produced radioisotope. To meet this endpoint we will make a direct comparison of the ⁶⁸GA-PSMA-cyclotron vs. ⁶⁸Ga-PSMA-generator scans obtained within 24-48h. We will measure SUVmean and SUVmax of the same Regions of Interest (ROI) in both scans using the PET analysis software we use in our clinical practice. The two scans will be retrieved and the exact same ROIs will be drawn at the same time for the two scans (software offers a copy-paste function so that no discrepancies exist between the two measurements). The SUVmean and SUVmax obtained from both scans for each Region of Interest will then be analyzed to determine the within-subject coefficient of variation value as measured by the Bland Altman analysis.

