11.2.5 Record Retention

Essential documents are those documents that individually and collectively permit evaluation of the study and quality of the data produced. After completion of the study, all documents and data relating to the study will be kept in an orderly manner by the Investigator in a secure study file. Essential documents should be retained for 2 years after the final marketing approval in an ICH region or for at least 2 years since the discontinuation of clinical development of the IP. In addition, all subjects medical records and other source documentation will be kept for the maximum time permitted by the hospital, institution, or medical practice.

12. Statistical Considerations

Up to 30 patients will undergo a dynamic whole-body scan with ^{68}Ga -PSMA_{Gen} and later ^{68}Ga -PSMA_{cyc} with a maximum time of 2 days and a minimum time of 6 h between the two injections. All 22 patients will receive ^{68}Ga -PSMA_{Gen} at a specific activity of 1-2 Ci/ μmol , the typical specific activity used in clinical trials with ^{68}Ga -PSMA. We expect the ^{68}Ga -PSMA_{cyc} to be delivered and injected at a specific activity of 0.1- 2.0 Ci/ μmol given the rigors of delivery. We will accept doses in this range as the prior small animal imaging was designed to understand the affect of specific activity over a 20X range.

For a power of 80% a calculation of the sample size needed to test odds ratio (equality test) was performed. A sample size of 22 would give a power percentage of 18.47 with a type 1 error of 5%. This power percentage is sufficient in providing confidence that the findings will reflect a true effect. The median statistical power of studies in the neurosciences is between ~8% and ~31%. We will not and should not be focusing on p-values but rather the estimates of the effect size with its confidence intervals.

Estimating repeatabilities using a mixed effects model framework has proven to be powerful, the repeatability (r) is calculated as the variance among group means (group-level variance) over the sum of group-level and data-level (residual) variance (v). A Pearson's correlation coefficient will demonstrate also present the repeatability of results. Intraclass correlation values for both groups will be calculated to test if the groups differ in repeatability. These collection of tests(functions) for estimating repeatability of measurements with a single grouping factor are all performed in R statistical software.

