To quantify the agreement between the two scans, we will use the repeated measures correlation coefficient to account for multiple observations per subject. We will calculate the repeated measures correlation-coefficient for the SUVmax and SUVmean for reference regions as well as regions suspicious for metastatic disease. We will measure SUVmean and SUVmax of the same Regions of Interest (ROI) in both scans using the PET analysis software we use in our clinical practice. The two scans will be retrieved and the exact same ROIs will be drawn at the same time for the two scans (software offers a copy-paste function so that no discrepancies exist between the two measurements). The SUVmean and SUVmax obtained from both scans for each Region of Interest will then be analyzed to determine the within-subject coefficient of variation value as measured by the Bland Altman analysis. If the agreement between the two scans lies within an acceptable rate (which we consider 30% based on previously published data), we will consider the two methods equivalent.

Also, as aforementioned the Bland-Altman Test presents proof of repeatability analysis.

13. Adverse Event Reporting Requirements

Adverse event (AE) monitoring and reporting is a routine part of every clinical trial. The investigator will be required to provide appropriate information concerning any findings that suggest significant hazards, contraindications, side effects, or precautions pertinent to the safe use of the drug or device under investigation. Safety will be monitored by evaluation of adverse events reported by subjects or observed by investigators or research staff, as well as by other investigations such as clinical laboratory tests, x-rays, electrocardiographs, etc.

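### The sample size rests on an odds-ratio test that the plan never uses, its 18.47% power is called sufficient beside an 80% target, and the paired 30% SUV criterion has no power or precision calculation at 22 or 30 patients

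*Combined protocol and SAP*

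**What the plan says.** Section 12 (Statistical Considerations) contains the only sample-size calculation. It begins "For a power of 80% a calculation of the sample size needed to test odds ratio (equality test) was performed" and reports "A sample size of 22 would give a power percentage of 18.47 with a type 1 error of 5" per cent. The next sentence is "This power percentage is sufficient in providing confidence that the findings will reflect a true effect". Support comes from a comparison with median power in neuroscience studies, given as roughly 8% to 31%. The paragraph closes with "We will not and should not be focusing on p-values but rather the estimates of the effect size with its confidence intervals".

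The primary endpoint in Section 1 is proof of equivalence between the two products. SUVmean and SUVmax are measured in the same regions on both scans and summarised by the "within-subject coefficient of variation value as measured by the Bland Altman analysis". Section 12 repeats this and adds a decision rule: "If the agreement between the two scans lies within an acceptable rate (which we consider 30% based on previously published data"), the two methods are declared equivalent. The other planned analyses are repeated-measures correlation, Pearson correlation, intraclass correlation and mixed-model repeatability.

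On numbers, Section 12 says "All 22 patients will receive" the generator product, while Section 1 says "30 patients will be enrolled in this study". Sections 1, 3.1 and 12 also say up to 30.

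**The concern.** There are three faults in one paragraph.

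- **The test does not belong to the design.** An odds ratio needs a binary outcome, and every planned analysis is of continuous paired SUVs. An equality test also asks the reverse of the primary question, which is equivalence.
- **The conclusion contradicts the target.** A calculation opened with an 80% target and returning 18.47% has missed it. On its own terms it would miss a true effect about 82% of the time (100 − 18.47). Typical power in another field does not make that enough for this trial.
- **The actual criterion has no calculation.** No within-subject CV is assumed, and no interval width or power is given. The figure of 30 patients has no calculation of any kind.

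The stake is the primary conclusion. Patients receive two research scans so that a yes/no statement on equivalence can be made, and nothing in the plan shows how likely that statement is to be right.

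**Working it through.** **1. The stated 18.47%.** The inputs given are 22, a 5% type 1 error, and an odds-ratio equality test. The odds ratio, the two proportions, the sidedness and whether 22 is total or per group are not given. With the usual Wald formula, power = Φ(|ln OR|/SE − z), where SE² = 1/(n·pA·qA) + 1/(n·pB·qB), many inputs return 18.47%. With a two-sided test and a reference proportion between 0.10 and 0.75, odds ratios of about 1.9 to 2.5 do so at 22 per group, and about 2.5 to 4.2 at 11 per group. The figure can be back-solved but not reproduced.

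**2. What the 80% target would need.** Whatever effect gives 18.47% at 22, the required number scales as follows.

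- Two-sided: the implied standardised effect is z(0.1847) + 1.960 = −0.898 + 1.960 = 1.062. Then N = 22 × [(1.960 + 0.842)/1.062]² ≈ 153. At 30, power is about 24%.
- One-sided: −0.898 + 1.645 = 0.747. Then N = 22 × [(1.645 + 0.842)/0.747]² ≈ 244. At 30, power is about 22%.

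**3. The paired criterion.** The documents give no CV, so CVs here are assumptions shown over a range. All figures take one SUV pair per patient and no dropout. Section 12 does not say which statistic must be within 30%, so four readings are worked. Here s is the observed within-subject CV (wCV), and chi-square has n − 1 degrees of freedom.

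- (a) Mean ratio: two one-sided 5% t-tests within 1/1.3 to 1.3 on the log scale, true ratio 1.0. The within-subject log SD is √ln(1 + CV²), and the SD of a paired difference is √2 times that (simulation).
- (b) Upper one-sided 95% limit of wCV below 30%: s must be below 30% × √(11.59/21) = 22.3% at n = 22, or 30% × √(17.71/29) = 23.4% at n = 30. At true CV 25% and n = 22, P(χ²₂₁ < 11.59 × (30/25)²) = P(χ²₂₁ < 16.69) = 27%.
- (c) Point estimate of wCV below 30%: at CV 25% and n = 22, P(χ²₂₁ < 21 × 1.44) = P(χ²₂₁ < 30.24) = 91%.
- (d) 95% limits of agreement, mean ± 1.96 SD, within 1/1.3 to 1.3 on the log scale (simulation).

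Chance of meeting the rule, n = 22 / n = 30:

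| True CV | (a) mean ratio | (b) upper limit of wCV | (c) wCV estimate | (d) limits of agreement |
|---|---|---|---|---|
| 10% | >99% / >99% | >99% / >99% | >99% / >99% | 23% / 21% |
| 15% | >99% / >99% | >99% / >99% | >99% / >99% | <1% / <1% |
| 20% | 99% / >99% | 80% / 91% | >99% / >99% | about 0 / about 0 |
| 25% | 92% / 98% | 27% / 35% | 91% / 94% | about 0 / about 0 |
| 30% | 78% / 92% | 5% / 5% | 54% / 53% | about 0 / about 0 |

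If the true ratio is 1.1, reading (a) falls to 70% / 82% at CV 25% and 56% / 69% at CV 30%. Under reading (c), a product pair whose true wCV is exactly 30% passes slightly more often than not.

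**4. Precision.** The 95% interval for wCV runs from 0.77 to 1.43 times the estimate at n = 22, and from 0.80 to 1.34 times at n = 30. The plan states neither these nor any target width.

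**The case against.** The strongest reply is that the plan disclaims p-values in favour of estimates with confidence intervals, and that 22 or 30 patients may well be enough. The second half stands. At a true wCV of 15% even reading (b) exceeds 99%, and at 20% it gives 80% / 91%, so the trial is not shown to be too small. The first half does not fill the gap. An estimation approach needs a planned precision, none is given, and Section 12 keeps a yes/no rule.

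A second objection is that the table depends on modelling choices. Converting 30% to 1/1.3 to 1.3 is stricter than a plain ±30%. For reading (d) at CV 10%, the plain scale gives about 53% / 56% instead of 23% / 21%. For reading (a) with 0.70 to 1.30 at CV 30%, it gives about 88% / 96%. These differences are real, but the spread remains: at CV 25%, reading (d) is about zero on either scale while reading (a) exceeds 90%. Readings (b) and (c) are closest to the plan's wording because it names the wCV, and they alone differ by 27% against 91% at n = 22. Reading (d) is less directly supported, although limits of agreement are the usual output of a Bland-Altman analysis.

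Third, the plan provides for several regions per patient, so one-pair figures are not the trial's operating characteristics. That is correct. They show only that the answer depends on choices the plan has not made.

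Finally, 22 is compatible with a ceiling of 30, for instance as the evaluable number. The plan does not say so, and other sentences give 30 as a fixed number.

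**Conclusion.** The concern holds and must be fixed. The only quantitative basis for the trial's size is the power of a test that will not be run. That power is 18.47% against a named 80%, and the sentence calling it sufficient contradicts the target. The paired 30% criterion has no power or precision at either stated number of patients.

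Two limits apply. The 18.47% is uncheckable, not shown to be an arithmetic error. The adequacy of 22 or 30 is undetermined, not disproved. Under the assumed CVs, one pair per patient and no dropout, the chance of meeting the rule at a CV of 25% runs from near 0% to above 90%, depending on what the 30% refers to. Confidence is high on the mismatch and the missing calculation, because both can be read directly from the plan.

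**What to change.** In Section 12, delete the odds-ratio calculation, the 18.47% figure, the sentence calling it sufficient and the neuroscience comparison. Replace them with the power or precision of the paired SUV criterion at one stated number of patients. State:

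1. the assumed within-subject CV as a range, with its source;
2. whether 30% applies to the mean ratio, the wCV point estimate, a confidence limit of the wCV (with its level) or the limits of agreement, and on which scale;
3. how multiple regions per patient, and SUVmean versus SUVmax, enter the calculation.

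Give evaluable and enrolled numbers separately and use them consistently in Sections 1, 3.1 and 12. Claim that 22 or 30 is adequate only once these points are fixed.

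The cost is one rewritten paragraph and an aligned patient number. The statistician and investigator must also settle the CV range, the statistic and the handling of regions. No new data or procedures are needed, and the restatement does not by itself change enrolment.

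### Section 12 plans r and ICCs with one unnamed grouping factor for data with patient, region and scan levels, and a per-product ICC would have no repeat scan behind it

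*Combined protocol and SAP*

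**What the plan says.** Section 12 (Statistical Considerations) defines the statistic: "the repeatability (r) is calculated as the variance among group means (group-level variance) over the sum of group-level and data-level (residual) variance". It adds that "Intraclass correlation values for both groups will be calculated to test if the groups differ in repeatability", and that the functions used are those "for estimating repeatability of measurements with a single grouping factor are all performed in R statistical software". The grouping factor is not named, the two groups are not defined, and nothing says whether regions are pooled or analysed one at a time.

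Later in section 12 the data are described: "We will measure SUVmean and SUVmax of the same Regions of Interest (ROI) in both scans". A repeated measures correlation is planned for "SUVmax and SUVmean for reference regions as well as regions suspicious for metastatic disease". That correlation is said to allow for several observations per subject; r and the ICCs get no such statement.

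The Study Design entry of the Protocol Summary says patients "will be administered a single intravenous dose of each of the study drugs", so there are two scans per patient and one per product. Equivalence is judged by a 30% limit on agreement, stated directly after the Bland-Altman within-subject CV. Section 1.2.1 lists confirmation of generator repeatability as a primary objective.

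**The concern.** The data have three levels: patient, region within patient, and scan. A variance ratio with one grouping factor must put every other source of variation in either the numerator or the residual. If regions are pooled and patient is the group, differences between organs enter the residual and can swamp scan-to-scan error. If patient-by-ROI is the group, the same organ differences enter the numerator and can hide scan-to-scan error and a systematic product difference. The same scans could then be reported as showing little or excellent repeatability, and the choice could be made after the data are seen.

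The ICC comparison raises a separate problem. If the groups are the two products, each ICC is computed from one scan per patient, and no scan is repeated with the same product.

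**Working it through.** **Plan's own figure.** There is none to reproduce: the documents give no expected r, ICC or variance component. The one calculated figure in section 12, 18.47% power for an odds-ratio test at n = 22, does not concern these statistics.

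**Inputs.** From the documents: two scans per patient, one per product; several ROIs of two kinds; the 30% limit, used here as an illustrative within-subject CV. Assumed, because the documents do not give them: K = 8 regions, the same ones in every patient, and three sets of log-scale SDs. Write Vp, Vt, Vpr and Ve for the patient, organ, patient-by-ROI and scan-to-scan variances, with Ve = ln(1 + CV²), and d for the log of the product ratio. At 30% CV, Ve = ln(1.09) = 0.0862.

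**Formulas** (expected one-way ANOVA ICC):
- Patient-by-ROI as group: r = (Vp + Vt + Vpr - d²/4) / (Vp + Vt + Vpr + Ve + d²/4).
- One region, patient as group: the same without Vt.
- Regions pooled, patient as group, d = 0: MSB = 2K·Vp + 2Vpr + Ve; MSW = [2(K-1)(Vt + Vpr) + (2K-1)Ve]/(2K-1); r = (MSB - MSW)/(MSB + (2K-1)MSW).

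**Set A** (organ 1.2, patient 0.2, patient-by-ROI 0.3), so Vt = 1.44, Vp = 0.04, Vpr = 0.09:
- By patient: MSB = 0.64 + 0.18 + 0.0862 = 0.906; MSW = (14/15)(1.53) + 0.0862 = 1.514; r = -0.608/(0.906 + 15 × 1.514) = -0.03. Using 4 or 12 regions instead of 8 gives -0.08 or -0.01.
- By patient-by-ROI: 1.57/1.6562 = 0.95. With a 1.3-fold product difference, d²/4 = 0.2624²/4 = 0.0172 and r = 1.5528/1.6734 = 0.93.
- One region: 0.13/0.2162 = 0.60. With the 1.3-fold difference, 0.1128/0.2334 = 0.48. Simulated data give slightly lower averages, 0.58 and 0.47.

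**Range over assumptions**, 30% CV, no product difference:

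| Organ / patient / patient-by-ROI SD | By patient | By patient-by-ROI | One region |
|---|---|---|---|
| A: 1.2 / 0.2 / 0.3 | -0.03 | 0.95 | 0.60 |
| B: 0.5 / 0.2 / 0.2 | 0.07 | 0.79 | 0.48 |
| C: 0.3 / 0.5 / 0.3 | 0.50 | 0.83 | 0.80 |

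Simulation gives 0.06 for B and 0.48 for C when grouped by patient.

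**Which set is plausible?** The documents give no SUVs. The dosimetry table in section 2.4.1 is a rough proxy. Absorbed dose per mCi is 0.969 for kidneys, 0.165 spleen, 0.114 liver, 0.0403 heart wall, 0.0389 muscle and 0.0340 red marrow. That is a 28-fold range with a log SD of 1.29 (0.97 over all 22 organs listed). Absorbed dose is not SUV and the reference regions are not named, so this makes wide organ spread credible but does not establish it.

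**ICC within one product, patient as group.** With one scan per patient, MSB = K·Vp + (Vpr + Ve) and MSW = Vt + (Vpr + Ve). Scan-to-scan error appears only in the sum Vpr + Ve and cannot be separated from real patient-by-region differences.
- Set A, CV 10% (Ve = 0.00995): (0.420 - 1.540)/(0.420 + 7 × 1.540) = -0.100.
- Set A, CV 30%: (0.496 - 1.616)/(0.496 + 7 × 1.616) = -0.095.

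Tripling the CV hardly moves it.

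**The case against.** **A per-region analysis is not excluded.** Single-factor functions are valid if run on one region at a time with patient as the group, and r then follows repeatability. By the one-region formula, with a between-patient CV of 30%, r is 0.90, 0.50 and 0.28 at within-subject CVs of 10%, 30% and 50%. This stands: the plan is open to a sound reading, but does not specify it.

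**A reader might infer that r will always be near 0 or near 1 and carry no information on repeatability.** The documents do not support that. It needs organs that differ far more than patients do, which they do not quantify in SUV. In set C, simulated r grouped by patient is 0.57, 0.49 and 0.39 at CVs of 10%, 30% and 50%, so it is intermediate and responsive.

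**A reader might also infer that r has a floor of 1/3**, by taking the variance of two-scan means literally. The plan's own parenthesis identifies that quantity as the group-level variance, in a mixed-model setting, so the ordinary variance component is the natural reading.

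**The two groups may not be the products.** They could be reference and suspicious regions, where two-scan ICCs can be compared. The text does not say, so the objection to the ICC comparison is conditional. If products are meant, one could argue that the patients and regions are the same, so the other components cancel. That assumes true uptake varies identically under both products, which is close to what the study sets out to show.

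**The consequence is limited.** The equivalence decision follows the Bland-Altman analysis, which section 12 also calls a repeatability analysis. That stands and limits the weight of this point.

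**Conclusion.** The concern holds in limited form. Section 12 applies a single-factor variance ratio to data with patient, region and scan levels without naming the factor. If regions are pooled, grouping alone moves r from about -0.03 to 0.95 under wide organ spread, from 0.06 to 0.79 at an organ SD of 0.5, and from 0.48 to 0.83 when patients differ more than regions. Under wide spread, pooled r stays at 0.93 with a 30% CV and a 1.3-fold product difference, while one-region r falls to 0.47. All these values rest on assumed variances.

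The ICC point does not depend on the assumed variances, only on which groups are meant. If they are the products, there is no same-product replicate, and comparing the two ICCs does not test whether repeatability differs.

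None of this alters the 30% equivalence rule. It matters because r and the ICC are named repeatability analyses and section 1.2.1 makes generator repeatability a primary objective. The plan should be changed, but its equivalence decision is not invalidated on this ground.

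**What to change.** Replace the single-factor r with one of these:
- a mixed model on log SUV, with product fixed and patient, patient-by-product scan, and ROI-within-patient random; or
- a per-region analysis with patient as the group.

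Report separately for lesions and for each reference region:
- the cyclotron/generator ratio with its confidence interval;
- the between-scan within-subject CV, from scan plus residual variance, with an interval clustered by patient.

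Both are needed. A CV from the residual alone omits scan-level error: a scan SD of 0.15 and a residual SD of 0.10 give about 10% from the residual, but √(0.15² + 0.10²) = 0.18, about 18%, between scans. With product fixed, the CV also omits any product difference, which the ratio supplies. Label the CV as variation between a generator scan and a cyclotron scan, since no product is repeated.

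Delete any test that the two products' ICCs differ. If an ICC is kept, define its groups and report it per region, as absolute agreement, beside the CV.

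The cost is SAP wording, with the same data and software. Reported agreement will look less favourable than a pooled ICC.

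### Section 12 uses correlation to measure agreement and repeatability, but both coefficients are unchanged when one product reads proportionally lower, so neither can support equivalence

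*Combined protocol and SAP*

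**What the plan says.** The Endpoints entry of the Protocol Summary sets the aim: "The primary endpoint of this study is to prove equivalence between the cyclotron and generator produced radioisotope". It describes the analysis as a within-subject coefficient of variation (wCV) of SUVmean and SUVmax from a Bland-Altman analysis, and does not mention correlation.

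Section 12 (Statistical Considerations) adds several statistics:

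- **Agreement:** "To quantify the agreement between the two scans, we will use the repeated measures correlation coefficient to account for multiple observations per subject". It is applied as follows: "We will calculate the repeated measures correlation-coefficient for the SUVmax and SUVmean for reference regions as well as regions suspicious for metastatic disease".
- **Repeatability:** a mixed-model variance ratio, and then "A Pearson's correlation coefficient will demonstrate also present the repeatability of results".
- **Intraclass correlation:** "Intraclass correlation values for both groups will be calculated to test if the groups differ in repeatability". The form of the ICC is not given.
- **wCV:** the paired SUVs are used to "determine the within-subject coefficient of variation value as measured by the Bland Altman analysis".
- **Decision:** the sentence after the wCV sentence opens "If the agreement between the two scans lies within an acceptable rate (which we consider 30% based on previously published data" and concludes that the methods are then equivalent. It calls the quantity being judged only the agreement between the scans.

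**The concern.** Equivalence of the two production routes means that they give the same SUV in the same region. Correlation asks something else: whether regions that are hotter on one scan are also hotter on the other. It does not register a scale difference between products, and a scale difference is the failure an equivalence study most needs to detect. Such a difference is plausible here. Section 12 accepts a specific activity of 0.1-2.0 Ci/µmol for the cyclotron product against 1-2 Ci/µmol for the generator product, and Section 7.11 says the order of products is not randomized.

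Section 12 does not call the correlations descriptive. One is the named measure of agreement and the other is presented as evidence of repeatability. A high value could be reported in either role whatever the true SUV ratio is.

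**Working it through.** **Inputs.** From the documents: the statistics named above, the 30% limit, and 22 or 30 patients (Section 12 uses both numbers). The documents give no expected correlation, so there is no planned figure to reproduce. The following are assumptions: 6 ROIs per patient, per-scan CV 5-20%, log-SD between ROIs 0.3-0.9, log-SD between patients 0.4, and 300 simulated trials per setting.

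**Step 1: invariance.** Let x be the SUV with one product and y the SUV with the other. Pearson r = cov(x, y) / [SD(x) SD(y)]. Replace y by ky with k > 0: the numerator becomes k cov(x, y), the denominator becomes k SD(x) SD(y), and k cancels. Repeated-measures correlation is the same ratio computed on values centred within each patient. Centring ky gives k times the centred y, so k cancels again. This holds for any data and needs none of the assumptions above.

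**Step 2: one product at half the other, no noise.** Both correlations are 1.000. With x = 1 and y = 0.5, the mean of the pair is 0.75 and the relative difference is -0.5 / 0.75 = -66.7%.

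**Step 3: what wCV does with the same data.**

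- Bias included: wCV = sqrt(mean[(d/m)²/2]), where d is the paired difference and m the pair mean. At ratio 0.5 this is 0.667 / 1.414 = 47.1%, above 30%.
- Bias removed: wCV = SD(d/m) / 1.414. A constant ratio gives SD(d/m) = 0, so wCV = 0%, below 30%.
- Bias included, ratio 0.70: d/m = -0.30 / 0.85 = -35.3%, and wCV = 0.353 / 1.414 = 25.0%, below 30%.
- Bias included, where it reaches 30%: (1 - k) / [(1 + k)/2] = 0.30 × 1.414 = 0.424, so k = (1 - 0.212) / (1 + 0.212) = 0.65.

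**Step 4: with noise.** 22 patients, between-ROI log-SD 0.6:

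| Scan CV | Repeated-measures r, ratio 1.0 | Same, ratio 0.5 | Pearson r, ratio 1.0 | Same, ratio 0.5 | wCV with bias, ratio 0.5 | wCV without bias, ratio 0.5 |
|---|---|---|---|---|---|---|
| 5% | 0.992 | 0.992 | 0.994 | 0.994 | 47.3% | 4.4% |
| 10% | 0.968 | 0.968 | 0.976 | 0.976 | 47.8% | 8.9% |
| 15% | 0.932 | 0.932 | 0.948 | 0.948 | 48.5% | 13.1% |
| 20% | 0.879 | 0.884 | 0.906 | 0.910 | 49.6% | 17.3% |

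The small differences between ratio columns are simulation error. Over all settings at ratio 0.5, repeated-measures r is 0.68-0.996 and Pearson r is 0.84-0.996. The same ranges occur at ratio 1.0. The low ends come from noise combined with a narrow SUV spread, not from bias. With 30 patients (run at 10% CV) the results are the same. At ratio 0.5, a wCV with bias included is below 30% in no run, and a wCV with bias removed is below 30% in every run.

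**Step 5: the ICC.** A one-way ICC that pools both products falls from 0.83-0.995 at ratio 1.0 to 0.26-0.68 at ratio 0.5 (raw SUV), so it does see the bias. An ICC computed separately within each product contains no between-product comparison and cannot. Section 12 does not say which is meant, and its reference to both groups can be read as the second.

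**The case against.** The strongest reply is that correlation does not drive the decision, and much of that reply stands. The Protocol Summary defines the primary endpoint analysis through wCV alone. In Section 12 the 30% sentence comes five sentences after the one that names the correlation, and directly after the wCV sentence. A limit to stay within suits a coefficient of variation and does not suit a correlation, where higher is better. Section 12 also says that attention should be on effect estimates with confidence intervals.

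A reader might therefore go too far in three ways:

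- **That equivalence will be declared on a correlation.** No rule in the documents does this, and the natural reading of the 30% is wCV.
- **That the whole plan would miss a twofold difference.** A wCV that includes bias would catch it, at 47%. An ICC across the two products would also fall sharply.
- **That the correlations must come out near 1.** That depends on how widely the ROIs spread relative to scan noise, which the documents do not give. If reference and suspicious regions are analysed separately, the spread would be narrower. What holds in general is that the value does not respond to bias.

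The reply does not make correlation a measure of agreement, which is the role Section 12 gives it. Nor does the text secure the protection that wCV could offer: it does not say whether wCV includes the between-product bias, and it does not name the statistic judged against 30%. The general remark about effect sizes does not specify any between-product mean difference or ratio with a confidence interval.

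**Conclusion.** Wrong as written, in a limited respect. The two correlations cannot do the work Section 12 assigns to them and cannot support equivalence. That is an algebraic identity and rests on no assumption beyond a constant ratio between products. The particular values of about 0.97 and 0.98 rest on the assumed noise and ROI spread.

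The documents do not support the stronger conclusion that the primary analysis is blind to bias. They leave that open: a product reading half the other would fail the 30% limit under one reading of wCV and pass it under another. Even on the bias-inclusive reading, a product reading 30% low gives 25.0% without noise and passes. So the correlations should be removed from the inference and the comparison between products made explicit.

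**What to change.** In Section 12:

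1. Label the repeated-measures and Pearson correlations as descriptive, and state that they do not inform the agreement, repeatability or equivalence conclusion.
2. As the agreement measure, report the cyclotron/generator geometric mean ratio of SUVmean and of SUVmax with its confidence interval. Obtain it from a mixed model for log SUV with a product term and random effects for patient and for ROI within patient. A patient-by-product random effect is worth adding, because all ROIs in one scan share that injection's error and the interval could otherwise be too narrow.
3. Report Bland-Altman bias and limits of agreement by a method that allows for several ROIs per patient.
4. State whether wCV includes the between-product bias, and name the statistic to which the 30% applies.
5. If a single index is wanted, use an absolute-agreement ICC or a concordance coefficient computed across the two products, not within each.

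The cost is Section 12 wording and a few lines of code. No new data, scans or patients are needed.
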